### 8.3. Collection, Storage and Analysis of Clinical Samples

In line with standard clinical care, each potential participant will provide a urine sample to test for pregnancy and a vaginal swab to screen for the presence of sexually transmitted infections. Samples provided will be handled, tested and destroyed in accordance with local clinic guidelines. The results will be used to assess eligibility. If a participant is randomised into the trial and subsequently the STI result comes back positive they will be treated for the STI as per standard of care and the result and treatment will be recorded in the DEBi CRF. The participant will continue on the trial.

#### 8.3.1. Return of unused trial medication

Participants will be asked to return their completed blister packs or unused medication to the recruiting clinic to confirm adherence to their treatment and for destruction of surplus trial drug. Blister packs should be returned in person at their standard review at 3 months after starting

treatment for problem bleeding. Where a participant is unable to attend a clinic in person, the NCTU will work with the participant to facilitate return of the IMP packs back to the recruiting site.

## 8.4. Withdrawal and discontinuation Procedures

### 8.4.1. Withdrawal prior to randomisation

Any patients that request to withdraw their consent **prior to randomisation** will be withdrawn completely from the trial; they will not be randomised, and follow-up questionnaires will not be issued.

### 8.4.2. Discontinuation and withdrawal post randomisation

Participants may withdraw from the trial for any reason. This will be made clear at recruitment. We will include a contact number for a member of staff at the recruiting clinic as a point of contact for participants to use in the event they are experiencing problems during the trial or considering early withdrawal.

The NCTU must be informed of all requests by participants to stop their involvement in the trial; appropriate action will be taken to ensure that the participant's wishes are followed promptly and safely.

Sites will be trained to determine which activities participants may wish to withdraw from.

Where a participant communicates their intention to withdraw from some or all of the main trial, the site must confirm whether they are also withdrawing consent for the long term follow-up.

**Table 8-Withdrawal type and procedure post randomisation**

Withdrawal type	Withdrawal procedure	Use of data
Withdrawal from trial treatment	Any participant that requests to discontinue trial treatment will be marked as withdrawn from treatment on the trial database but will be asked to continue to complete questionnaires if willing. Information on reason for stopping trial treatment will be recorded by the site if given, and patient care will continue as part of standard clinical practice.	Any data collected prior to participant withdrawal will be retained and used in the analysis.
Removal of implant	Any participant who notifies the trial or site team that their implant has been removed during their participation in the trial would be withdrawn from the trial and unblinded to their treatment allocation to	Any data collected prior to participant withdrawal will be retained and used in the analysis.

	inform their ongoing contraceptive care. Participants would not be required to complete any further questionnaires or daily diaries but would be followed up for safety outcomes for 7 days following stopping of their trial treatment.	
Withdrawal from daily bleed diary	Any participant that requests to discontinue from daily bleed diary will be marked as withdrawn from diary collection on the trial database and no further MyCap notifications will be sent. Withdrawal from the daily diary does not withdraw from questionnaire completion.	Any data collected prior to participant withdrawal will be retained and used in the analysis.
Withdrawal from follow up questionnaires	Any participant that requests to discontinue from trial questionnaires will be marked as withdrawn from questionnaire collection on the trial database and no further contact relating to questionnaires will be made. Withdrawal from questionnaires does not withdraw from daily diary completion.	Any data collected prior to participant withdrawal will be retained and used in the analysis.
Withdrawal from long-term follow-up	Any participant that withdraws consent for the long term follow-up will be recorded within the database and no long term follow-up data will be collected.	Any data collected prior to participant withdrawal will be retained and used in the analysis.
Complete withdrawal- from trial treatment, daily bleed diary, follow up questionnaires and long-term follow up	Any participant that requests complete withdrawal will be marked as withdrawn and no further contact will be made.	Any data collected prior to participant withdrawal will be retained and used but all participant information will be redacted (marked with xxs) and no further contact will be made.

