## 1. Background and Rationale

Safe and effective interventions for people with irregular bleeding whilst using long-acting reversible contraceptives (LARCs) has been identified as the number 5 priority by The James Lind Alliance Contraception Priority Setting Partnerships. The 68mg etonogestrel subdermal contraceptive implant (implant) is the most effective (failure rate 0.05%) and popular method of LARC in the UK accounting for 40% of LARC and 18% of overall contraception used [2, 3]. The implant is a small flexible tube, placed under the surface of a patient's skin in the upper arm, with each implant providing contraception for up to three years. Unfortunately, the etonogestrel implant has the least favourable bleeding pattern of all LARC methods with 24% of users experiencing problem or unscheduled bleeding once the implant has been inserted. Problem bleeding is the most commonly reported reason for discontinuation of the implant, with 25% of users choosing to have the implant removed early due to their problem bleeding [4-7].

Current evidence for the best treatment for problem bleeding whilst using the implant is limited. To date, research has explored the use of the COCP, non-steroidal anti-inflammatory drugs (NSAIDs), Doxycycline and Tamoxifen with mixed results, and several important contraindications excluding some implant users from the use of these agents. The COCP is the recommended first line treatment in UK national guidelines [8] for problem bleeding when using the implant. The COCP works by the estrogen component of COCP sustaining endometrial integrity which counteracts the progestin-induced decidualisation and endometrial atrophy that creates problem bleeding.

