### 2.3. Secondary Objectives and Outcome Measures

**Table 2-Secondary Objectives**

Objective	Outcome Measure	Time Point	Method of Collection
To establish if the proportion of participants reporting problem bleeding is not worse in participants treated with desogestrel compared to COCP.	Participant self-reported significant improvement in the bleeding pattern.	Day 30 and 60	Participant Questionnaire
	Longest duration of consecutive non-bleeding (no bleeding or spotting) whole	Daily	Daily bleeding diary

	days for each 30-day period within the 90 days.		
To determine the effect of desogestrel compared with COCP on total number of non-bleeding, spotting and bleeding days during the 90-day treatment period	Participant self-reported bleeding pattern.	Daily	Daily bleeding diary
To determine the effect of desogestrel compared with COCP on the number and duration of bleeding episodes (one or more consecutive days of bleeding, bounded by bleed-free days) within the 90 days	Participant self-reported bleeding pattern.	Daily	Daily bleeding diary
To determine the effect of desogestrel compared with COCP on the time to the longest consecutive non-bleeding days	Participant self-reported bleeding pattern.	Daily	Daily bleeding diary
To determine the acceptability with trial treatment	Participant-reported side effects	Day 30, 60 and 90	Participant Questionnaire
To establish participant adherence to treatment	Participant reported adherence to trial treatment	Daily	Daily bleeding diary
	Participant reported discontinuation/removal of their implant	Day 30, 60 and 90	Participant Questionnaire
To determine the effect of desogestrel and COCP on participant Quality of life	Participant reported EQ-5D-5L and ICECAP-A	Day 30, 60 and 90	Participant Questionnaire

WPD 3.1\_Protocol Template\_Version 3.1\_20-Apr-2023

To determine the cost of treating implant user problem bleeding with desogestrel or the COCP	Treatment and healthcare usage	Day 30, 60 and 90	Participant Questionnaire
To determine the proportion of participants who intend to continue their allocated treatment.	Participant reported	Day 90 or sooner if early withdrawal from trial	Participant Questionnaire

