### 8.2.11. 90-day Follow-up Questionnaires

Participants will complete a questionnaire (online, postal or telephone) at 90 days after randomisation which will collect information on the following:

- Bleeding days and episodes
- Perception of their bleeding pattern
- Treatment acceptability
- Global impression of treatment
- Reporting of symptoms and known treatment side effects
- Medications
- Use of health service resources relating to problem bleeding or contraceptive use
- Out of pocket expenses for treatments or products in relation to problem bleeding
- Health Related Quality of life (EQ-5D-5L)
- Capacity-wellbeing (ICECAP-A)
- Intention to continue using implant and allocated trial treatment

At the end of the 90-day participation period, participants will be unblinded to their treatment allocation by their recruiting site. Unblinding will take place at the 3-month standard care visit, or for participants who are unable/unwilling to attend a clinic visit, the recruiting centre will call the participant to reveal their treatment allocation over the telephone. The recruiting centre will be asked to confirm whether the participant intends to continue with their implant and allocated trial treatment (as part of their standard care) once their participation in the trial has concluded.

Completion windows for 30-, 60- and 90-day questionnaires will be 10 days. Questionnaires will no longer be available for completion once outside of the specified completion window; therefore, no protocol deviations will be required for completion of data outside of the specified data collection windows.

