### 14.3. Analysis of Outcome Measures

The reporting of the trial will be in accordance with the CONSORT extension to reporting of non-inferiority and equivalence randomised trials [24]. Full details of the statistical analysis will be provided in the Statistical Analysis Plan, which will be finalised and approved by the Trial Steering Committee (TSC) prior to database lock.

Comparative analysis will be performed for the primary outcome on both the intention to treat (ITT) population and some version of the per-protocol (PP) population (preferably complier average causal effect (CACE) analysis, if feasible/identified), as a protection against the ITT's possible increased risk of falsely claiming noninferiority (type I error). Primary estimand will be the treatment policy estimand (i.e., ITT population- analysing data on all randomised participants according to the randomised groups irrespective of subsequent compliance with the treatment allocation) with CACE (or per-protocol) results used to check the consistency. Full definition and cut-off for compliance will be specified in the Statistical Analysis Plan (SAP).

For the primary outcome, a two-sided 95% confidence interval for the between-group difference in proportion of participants reporting significant improvement will be constructed by fitting a mixed-effect logistic regression model, adjusting for site as a random effect and other minimisation factors as fixed effects. The model will include outcome data from all the 3 timepoints (30, 60, and 90 days) and will include treatment by time interaction to obtain the treatment effect at each timepoint with 90 days as the primary contrast. Estimates of model-adjusted difference in proportions and 95% confidence intervals will be obtained by contrasts of average marginal predictions in the fitted model. Non-inferiority of desogestrel will be inferred if the lower bound of this interval lies within the non-inferiority margin of 10%. Missing data for primary outcome will be dealt with through maximum likelihood estimation using mixed-effect model which will use all available follow-up data. Intercurrent events such as discontinuation of assigned treatment or treatment switching, if any, will be dealt with through treatment policy strategy for the primary analysis.

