#### 14.4.4. Procedures for missing, unused and spurious data

Every effort will be made to follow up all participants up to the primary endpoint, however, as missing data is inevitable, we will employ statistical techniques for handling missing data for the primary outcomes under the Missing At Random assumption such as further adjustment in the mixed model for variables predictive of missingness. For the primary analysis, only minimisation variables will be adjusted for as covariates and we do not expect any to be missing as they are required for the participant to be allocated.

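### Stopping questionnaires at implant removal contradicts the treatment-policy estimand and leaves plausibly outcome-related gaps that are analysed as missing at random; the bias depends on unstated removal rates

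*Protocol*

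**What the plan says.** Protocol Table 8 (section 8.4.2) says that a participant who reports that "their implant has been removed during their participation in the trial would be withdrawn from the trial" and is unblinded. It continues: "Participants would not be required to complete any further questionnaires or daily diaries". Only 7 days of safety follow-up remain, and data collected before removal are kept. The row does not ask for a reason. In the same table, a participant who only stops trial treatment "will be asked to continue to complete questionnaires if willing", and the reason is recorded if given.

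The primary outcome is the day-90 answer on the five-point scale, reduced to significantly improved or not (section 14.2.1). Section 14.3 sets a treatment-policy estimand in all randomised participants. Its examples of intercurrent events are stopping the assigned treatment and switching treatment; implant removal is not among them. On gaps it says: "Missing data for primary outcome will be dealt with through maximum likelihood estimation using mixed-effect model which will use all available follow-up data". Site is the only random effect named. Section 14.4.4 describes techniques for "handling missing data for the primary outcomes under the Missing At Random assumption".

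Section 1 states: "Problem bleeding is the most commonly reported reason for discontinuation of the implant". It adds that 25% of users have the implant removed early for bleeding, with no period given.

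Table 2 lists "Participant reported discontinuation/removal of their implant" at days 30, 60 and 90. The 30- and 60-day questionnaire list (8.2.10) contains removal. The 90-day list (8.2.11) has only "Intention to continue using implant and allocated trial treatment".

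**The concern.** A treatment-policy estimand uses the outcome whatever happens after randomisation. Table 8 stops seeking that outcome for one event, and that event is plausibly tied to the outcome: everyone enrolled has problem bleeding, and the protocol's own background makes bleeding the leading reason for removal. The likelihood analysis then treats a removed participant like others in the same arm with the same covariates and, at most, the same earlier answers.

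At stake is the one-sided 2.5% error rate of the non-inferiority claim. If more people on desogestrel give up the implant because bleeding has not settled, those people drop out of the comparison and the deficit shrinks. The SAP can add analyses, but it cannot recover answers or reasons for removal that were never requested.

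**Working it through.** **1. The plan's own figure.** Inputs from section 14.1: 85% in both arms, margin 10 points, one-sided 2.5%, 90% power, Farrington-Manning score test. The formula gives 275.7, so 276 per arm and 552 in total; 552/0.80 = 690. The plan's figures reproduce.

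**2. What the model gives a removed participant.** With site as the only random effect, a participant's day-30 and day-60 answers do not inform that participant's own day-90 value. A removed participant therefore counts, in effect, at about the arm's observed rate: 0.85 on the planning assumption. The same holds in any model for removal before day 30. If the SAP adds a participant random intercept (assumed SD 1 to 3; assumed rates of 65%, 75% and 85% at days 30, 60 and 90), the value is 0.79 to 0.64 after one answer short of significant improvement, and 0.71 to 0.47 after two.

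**3. Error rate at the margin, 85% as the COCP rate with removals counted as failures.** Assumptions: true rates 85% and 75%, 276 analysed per arm, removal before any informative answer. Let r be the removal rate in an arm.

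Estimated rate = true rate/(1 − r)

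P(non-inferiority) = Φ((d + 0.10)/SE − 1.96), where d is the estimated difference (desogestrel minus COCP) and SE = √[(pC(1 − pC) + pD(1 − pD))/276]

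- Removal 3% COCP, 6% desogestrel: 0.85/0.97 = 0.876 and 0.75/0.94 = 0.798. d = −0.078, SE = 0.0313, P = 10%.
- Removal 5% and 10%: 0.85/0.95 = 0.895 and 0.75/0.90 = 0.833. d = −0.061, SE = 0.0291, P = 26%.
- Removal 10% and 10%: 0.944 and 0.833. d = −0.111, which is conservative.

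**4. The same check with 85% as the COCP rate among those not removed.** The true difference, removals counted as failures, is again −10 points. For 5% and 10%: COCP 0.85 × 0.95 = 0.8075; desogestrel 0.8075 − 0.10 = 0.7075; observed desogestrel rate 0.7075/0.90 = 0.786; d = 0.786 − 0.850 = −0.064; SE = 0.0327; P = 19.6%. The last column credits removed participants with 65% of the arm's observed rate, to represent a model in which earlier answers pull the value down.

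| Removal COCP / desogestrel | Bias, points | P, arm's rate | P, 65% of arm's rate |
|---|---|---|---|
| 5% / 5% | −0.5 | 1.7% | 2.0% |
| 10% / 10% | −1.1 | 1.1% | 1.5% |
| 10% / 5% | −5.0 | below 0.1% | 0.2% |
| 5% / 7.5% | +1.5 | 6.5% | 4.7% |
| 5% / 10% | +3.6 | 19.6% | 10.2% |

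The bias column refers to the arm's-rate case; positive values favour non-inferiority. Counting removals as failures gives 2.5% in every row, by construction.

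**5. Power cost of counting every removal as failure.** With no true difference and 276 analysed per arm, rates of 0.85 × 0.95 = 0.8075 or 0.85 × 0.90 = 0.765 in both arms give power of about 85% or 79%, against about 90% with no removals.

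**The case against.** A reader might infer that the test leans towards non-inferiority in general. The documents do not support that. No 90-day removal rate is given for either arm, and the 25% in section 1 has no period. Equal removal gives an error rate slightly below 2.5%, and more removal on COCP penalises desogestrel. The condition for inflation is plausible, since section 1.1 expects desogestrel to be no more effective than COCP and perhaps slightly less, but nothing fixes its size.

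A reader might also infer that removals are known failures scored as successes. That goes too far. Bleeding is the commonest reason for removal, not the only one. The implant is the presumed source of the bleeding, so a participant might honestly report significant improvement once it is out. Treating removal as failure is a choice of estimand, and the error rates above measure distance from that choice. There is no explicit imputation step, and a participant-level term in the SAP would weaken the implicit credit.

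Two further objections carry weight. Treatment policy is defined in section 14.3 by compliance with the allocated treatment, and the implant is not the allocated treatment, so its reach is arguable; that is a reason to name the event. Sensitivity analyses belong in the SAP, and removal is a secondary outcome, so an imbalance would be seen. Neither supplies the missing answers.

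The gap in the 90-day list does not drive the primary bias: Table 8 acts only when removal is notified, so an unreported late removal leaves the day-90 questionnaire in place. It affects the secondary outcome, including the time to removal required by Table 10.

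**Conclusion.** The point holds in a conditional form. Table 8 stops outcome collection at implant removal, in conflict with the stated estimand and with its own handling of treatment withdrawal. It leaves gaps that Missing At Random may not cover. False non-inferiority at the margin is about 10% at 3% and 6% removal and 20% to 26% at 5% and 10%, falling to about 10% for the latter pair under the 65% assumption. These figures rest on assumed removal rates, 276 analysed per arm, and removal counted as failure. Equal or reversed removal gives no inflation. The firm part is the contradiction and the loss of data; the size and direction of the bias cannot be settled from the protocol.

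**What to change.** - **Table 8, removal row:** ask participants to continue the bleeding-pattern questionnaires through day 90 if willing, as for withdrawal from treatment, and record the date and reason for removal. The clinical handling in that row need not change.
- **Section 14.3:** name implant removal as an intercurrent event under the treatment-policy strategy. Pre-specify a sensitivity analysis that counts removal for bleeding or side effects before day 90 as not significantly improved.
- **Section 8.2.11:** add removal of the implant to the 90-day list, to match Table 2.

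The cost is a few more follow-up contacts, some answers given after unblinding, and one extra analysis. Answers after removal may also reflect the removal itself, which is why the sensitivity analysis is needed beside the main one. Making the failure rule primary is not recommended: it would change the stated estimand and cost the power shown above. The change helps only participants still in follow-up when it takes effect, so it should be made early.

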### 8.5. Post Trial Care

Participants will be given a voucher on completion of the 30-, 60- and 90-day questionnaires as a thank you for their time.

Usual care will continue after trial completion and unblinding, treatment outside of the trial will not be funded by the trial sponsor as both trial medications are licensed and readily available via GP or sexual health clinics and not limited, unless for medical reasons e.g. a new contraindication to the treatment.

## 9. Adverse Event Reporting

### 9.1. Reporting Requirements

The collection and reporting of Adverse Events (AEs) will be in accordance with the Medicines for Human Use Clinical Trials Regulations 2004 (and subsequent amendments). Definitions of the different types of AEs are listed in Table 9 below. AEs will be reported by the participants to the NCTU on the 30, 60 and 90 day questionnaires. The Principal Investigator will assess the seriousness and causality (relatedness) of all SAEs experienced by the participant with reference to the Reference Safety Information when notified of a participant SAE at their site.

**Table 9-Adverse Event Definitions**

Adverse Event (AE)	Any untoward medical occurrence in a clinical trial participant administered a medicinal product and which does not necessarily have a causal relationship with this treatment. Comment: An AE can therefore be any unfavourable and unintended sign (including abnormal laboratory findings), symptom or disease temporally associated with the use of an investigational medicinal product, whether or not related to the investigational medicinal product.
Adverse Reaction (AR)	All untoward and unintended responses to an IMP related to any dose administered. Comment: An AE judged by either the reporting Investigator or Sponsor as having causal relationship to the IMP qualifies as an AR. The expression reasonable causal relationship means to convey in general that there is evidence or argument to suggest a causal relationship.
Serious Adverse Event (SAE)	Any untoward medical occurrence or effect that: 
 
• Results in death
 
• Is life threatening*
 
• Requires hospitalisation or prolongation of existing hospitalisation
 
• Results in persistent or significant disability or incapacity
 
• Is a congenital anomaly/birth defect
 
• Or is otherwise considered medically significant by the Investigator**
 
 Comments:

	
The term severe is often used to describe the intensity (severity) of a specific event. This is not the same as serious, which is based on participants/event outcome or action criteria.
 
* Life threatening in the definition of an SAE refers to an event in which the participant was at risk of death at the time of the event; it does not refer to an event that hypothetically might have caused death if it were more severe.
 
** Medical judgment should be exercised in deciding whether an AE is serious in other situations. Important AEs that are not immediately life threatening or do not result in death or hospitalisation but may jeopardise the participant or may require intervention to prevent one of the other outcomes listed in the definition above, should be considered serious.

Serious Adverse Reaction (SAR)	An Adverse Reaction which also meets the definition of a Serious Adverse Event
Unexpected Adverse Reaction (UAR)	An AR, the nature or severity of which is not consistent with the applicable product information (e.g. Investigator Brochure for an unapproved IMP or Summary of Product Characteristics (SPC) for a licensed product). When the outcome of an AR is not consistent with the applicable product information the AR should be considered unexpected.
Suspected Unexpected Serious Adverse Reaction (SUSAR)	A SAR that is unexpected i.e. the nature, or severity of the event is not consistent with the applicable product information. A SUSAR should meet the definition of an AR, UAR and SAR.

